## 11. DESCRIPTION OF GLOBAL AMENDMENTS

### 11.1 GLOBAL AMENDMENT 1

Date of amendment	27 May 2019
EudraCT number	2019-000468-36
EU number	
BI Trial number	1346-0039
BI Investigational Medicinal Product(s)	BI 425809
Title of protocol	A study to investigate the effects of memantine on the pharmacokinetics of BI 425809 and vice versa in healthy male and female subjects (non-randomized, single-arm, open-label, three-period, one fixed sequence cross-over study)
To be implemented only after approval of the IRB / IEC / Competent Authorities	
To be implemented immediately in order to eliminate hazard – IRB / IEC / Competent Authority to be notified of change with request for approval	
Can be implemented without IRB / IEC / Competent Authority approval as changes involve logistical or administrative aspects only	
Section to be changed	1. Flow Chart 2. Section 3.1 3. Section 5.2.8.1.7 4. Appendix 1.1
Description of change	1. a) Errors in the planned times and time points of the C-SSRS assessments were corrected. b) By mistake, 3 memantine PK samples on day 10, period 3, visit 4 at 219:30, 220:30 and 221:00 were not entered in the Flow Chart of the CTP 1.0. This was corrected. 2. The size of possible cohorts was added and the risk assessment of this design was further specified. 3./4. The Screening version of the C-SSRS was replaced by the Screening/Baseline version of the C-SSRS as this is the correct version to be used.
Rationale for change	Based on EC feedback section 3.1 was revised as recommended. 3 PK samples of memantine were added that were by mistake not included in the original CTP. This correction was needed to align the sampling scheme for memantine in order to guarantee comparability of

Proprietary confidential information © 2019 Boehringer Ingelheim International GmbH or one or more of its affiliated companies

	profiles following administration of memantine alone and in combination with BI 425809. In addition, some errors/typos were corrected.
--	--

## 11.2 GLOBAL AMENDMENT 2

Date of amendment	19 July 2019
EudraCT number	2019-000468-36
EU number	
BI Trial number	1346-0039
BI Investigational Medicinal Product(s)	BI 425809
Title of protocol	A study to investigate the effects of memantine on the pharmacokinetics of BI 425809 and vice versa in healthy male and female subjects (non-randomized, single-arm, open-label, three-period, one fixed sequence cross-over study)
To be implemented only after approval of the IRB / IEC / Competent Authorities	
To be implemented immediately in order to eliminate hazard – IRB / IEC / Competent Authority to be notified of change with request for approval	
Can be implemented without IRB / IEC / Competent Authority approval as changes involve logistical or administrative aspects only	
Section to be changed	1. Title page 2. Flow chart 3. Table 5.2.5: 1 4. Section 5.2.3
Description of change	1. Clinical Trial Leader was changed to new contact details were provided. 2. In the listing of SCR procedures under footnote 1, visual tests and C-SSRS were missing. Footnote 8 was missing for the PK sample on Day 2, Visit 2. These were corrected. 3. A reference to the pregnancy test, indicating that tests are to be done as per footnote 5 in the Flow Chart, was missing. This was corrected. 4. For visual tests, a reference to any time point as per the Flow Chart was added instead of SCR and EOT.
Rationale for change	1. The study has been handed over to 2./3. Addition of the missing data. 4. Correction of errors/typos.

2. LIST OF ABBREVIATIONS

Term	Definition / description
AE	Adverse Event
AESI	Adverse event of special interest
ALT	Alanine aminotransferase
ANOVA	Analysis of variance
AST	Aspartate aminotransferase
$AUC_{\tau,ss}$	area under the concentration-time curve of the analyte in plasma at steady state over a uniform dosing interval τ
BI	Boehringer Ingelheim
BP	Blood pressure
$C_{max,ss}$	maximum measured concentration of the analyte in plasma at steady state over a uniform dosing interval τ
CTP	Clinical Trial Protocol
CTR	Clinical Trial Report
CV	Arithmetic coefficient of variation
C-SSRS	Columbia Suicidal Severity Rating scale
ECG	Electrocardiogram
gCV	geometric coefficient of variation
gMean	Geometric mean
ICH	International Conference On Harmonisation
IPD	Important protocol deviations
IQRMP	Integrated quality and risk management plan
MedDRA	Medical Dictionary For Regulatory Activities
PK	Pharmacokinetics
PKS	Pharmacokinetic parameter set
PR	Pulse rate
RAGe	Report appendix generator
RPM	Report planning meeting
SAE	Serious adverse event
SD	Standard Deviation
SOC	System Organ Class
TS	Treated set
TSAP	Trial Statistical Analysis Plan

Term	Definition / description
ULN	Upper limit of normal range

3. INTRODUCTION

As per ICH E9 ([1](#)) the purpose of this document is to provide a more technical and detailed elaboration of the principal features of the analysis described in the CTP, and to include detailed procedures for executing the statistical analysis of the primary variables and other data.

This TSAP assumes familiarity with the CTP and its amendments. In particular, the TSAP is based on the planned analysis specification as written in CTP Section 7 "Statistical Methods and Determination of Sample Size". Therefore, TSAP readers may consult the CTP for more background information on the study, e.g., on study objectives, study design and population, treatments, definition of measurements and variables, planning of sample size, randomisation.

Study data will be stored in a trial database within Medidata Rave system.

The statistical analyses will be performed within the validated working environment CARE, including SASTM (current Version 9.4, by SAS Institute Inc., Cary, NC, USA), and a number of SASTM-based tools (e.g., macros for the analyses of AE data or laboratory data; Report Appendix Generator system (RAGe) for compilation/formatting of the CTR appendices).

PK parameters will be calculated using Phoenix WinNonlinTM software (version Phoenix 6.3, Certara USA Inc., Princeton, NJ, USA).

4. CHANGES IN THE PLANNED ANALYSIS OF THE STUDY

All analyses described in this TSAP are in accordance with the statistical methods described in the revised CTP.

5. ENDPOINTS

5.1 PRIMARY ENDPOINTS

Primary endpoints are PK endpoints of BI 425809 and memantine, as defined in Section 2.1.2 of the CTP:

- $AUC_{\tau,ss}$ (area under the concentration-time curve of the analyte in plasma at steady state over a uniform dosing interval τ)
- $C_{max,ss}$ (maximum measured concentration of the analyte in plasma at steady state over a uniform dosing interval τ)

5.2 SECONDARY ENDPOINTS

5.2.1 Key secondary endpoints

Not applicable.

5.2.2 Secondary endpoints

Not applicable.

5.3.2 Safety parameters

Safety and tolerability of BI 425809 will be assessed based on further safety parameters defined in Section 2.2.2.2 of the CTP:

- *Adverse events (including clinically relevant findings from the physical and neurological examination)*
- *Safety laboratory tests*
- *12-lead ECG (only abnormal findings will be reported as AE)*
- *Visual tests (only abnormal findings will be reported as AE)*
- *Vital signs (blood pressure, pulse rate)*
- *Suicidality assessment (C-SSRS)*

6.2 IMPORTANT PROTOCOL DEVIATIONS

Consistency check listings (for identification of deviations from time windows) and a list of protocol deviations (e.g. deviations in drug administration, in blood sampling times, etc.) will be provided to be discussed at the Report Planning Meeting (RPM). At this meeting, it will be decided whether a discrepant data value can be used in the analyses or whether it must be corrected in the clinical database. Each protocol deviation must be assessed to determine whether it is an important PD (IPD). For definition of IPDs, and for the process of identification of these, refer to the BI reference document "Identify and Manage Important Protocol Deviations (IPD)" [\(2\)](#).

If any IPDs are identified, they are to be summarised into categories and will be captured in the decision log. Categories which are considered to be IPDs in this trial are defined in the integrated quality and risk management plan (IQRMP). If the data show other IPDs, the definition in the IQRMP will be supplemented accordingly by the time of the RPM.

IPDs will be summarized and listed. [Table 6.2: 1](#) below specifies which kind of IPDs could potentially lead to exclusion from which analysis set. The decision on exclusion of subjects from analysis sets will be made at the latest at the RPM, after discussion of exceptional cases and implications for analyses. If the data show other IPDs, this table will be supplemented accordingly by the time of the RPM.

Table 6.2: 1 Handling of IPDs

IPD code	IPD Category & Brief Description	Excluded from which analysis set
A1	Inclusion Criteria Not Met	PKS
A2	Exclusion Criteria Not Met	PKS
B1	Informed consent not available/not done	TS, PKS
B2	Informed consent too late	None
C1	Non-compliance	PKS
C2	Incorrect trial medication taken	PKS
C3	Incorrect intake of trial medication	PKS
C4	Improper washout between treatments	PKS
D1	Prohibited medication use	PKS
D2	Improper washout of concomitant medication	PKS
E1	Certain violations of procedures used to measure primary or secondary data	PKS
F1	Certain violations of time schedule used to measure primary or secondary data	PKS
G1	PDs affecting safety and rights of subjects	None

6.3 SUBJECT SETS ANALYSED

Subject sets will be used as defined in the CTP, Section 7.3.

Table 6.3: 1 Subject sets analyzed

Class of endpoint	Subject set	
	TS	PKS
Primary PK endpoints		X
Safety parameters & treatment exposure	X	
Demographic/baseline endpoints	X	

6.5 POOLING OF CENTRES

This section is not applicable, because the study was performed in only one centre.

6.6 HANDLING OF MISSING DATA AND OUTLIERS

Data of screened subjects who were withdrawn from the trial prior to first administration of any study drug will not be reported in the CTR.

Data of subjects who failed to complete all periods of the study (dropouts or withdrawals) will be reported in the CTR as far as their data are available. All withdrawals will be documented and the reason for withdrawal reported in the CTR.

CTP: *It is not planned to impute missing values for safety parameters.*

One exception where imputation might be necessary for safety evaluation are AE dates. Missing or incomplete AE dates are imputed according to BI standards (3).

Missing data and outliers of PK data are handled according to BI standards (4) and (5).

CTP: *PK parameters that cannot be reasonably calculated based on the available drug concentration-time data will not be imputed.*

6.7 BASELINE, TIME WINDOWS AND CALCULATED VISITS

Baseline is defined as the last available value before first study drug administration.

Time windows are defined in Section 6.1 of the CTP. Adherence to time windows will be checked at the RPM.

7. PLANNED ANALYSIS

The format of the listings and tables will follow the BI guideline "Reporting of clinical trials and project summaries" (6).

The individual values of all subjects will be listed. Listings will be sorted by sequence group subject number and visit (if visit is applicable in the respective listing). AE listings will be sorted by assigned treatment (see [Section 7.8.1](#) below for details). The listings will be contained in Appendix 16.2 (SDL) of the CTR.

The following standard descriptive statistical parameters will be displayed in summary tables of continuous variables:

N	number of non-missing observations
Mean	arithmetic mean
SD	standard deviation
Min	minimum
Median	median
Max	maximum

For plasma concentrations as well as for all PK parameters the following descriptive statistics will additionally be calculated:

CV	arithmetic coefficient of variation
gMean	geometric mean
gCV	geometric coefficient of variation

For PK parameters the following descriptive statistics will additionally be calculated:

P10	10 th percentile
Q1	1 st quartile
Q3	3 rd quartile
P90	90 th percentile

The data format for descriptive statistics of plasma concentrations will be identical with the data format of the respective concentrations. The descriptive statistics of PK parameters will be calculated using the individual values with the number of decimal places as provided by the evaluation program. Then the individual values as well as the descriptive statistics will be reported with three significant digits in the CTR.

Tabulations of frequencies for categorical data will include all possible categories and will display the number of observations in a category as well as the percentage (%) relative to the respective treatment group. Percentages will be rounded to one decimal place. The category missing will be displayed if and only if there actually are missing values. Percentages will be based on all subjects in the respective subject set whether they have non-missing values or not.

7.1 DEMOGRAPHIC AND OTHER BASELINE CHARACTERISTICS

Only descriptive statistics are planned for this section of the CTR.

7.2 CONCOMITANT DISEASES AND MEDICATION

Concomitant diseases will be coded according to the most recent version of MedDRA. Concomitant medication will be coded according to the most recent version of the World Health Organisation – Drug Dictionary. Concomitant non-drug therapies will be coded according to the most recent version of MedDRA.

A medication will be considered concomitant, if it

- is ongoing at the time of first study drug administration, or
- starts within the analysis phase of the respective treatment (see [Section 6.1](#) for a definition of treatments and analysis phases).

The relevance of the concomitant therapies to the evaluation of PK will be decided no later than at the RPM.

Only descriptive statistics are planned for this section of the CTR.

7.3 TREATMENT COMPLIANCE

Treatment compliance will not be analyzed as a specific endpoint. Any deviations from complete intake will be addressed in the Report Planning Meeting (cf. [Section 6.2](#)) and described in the CTR.

7.4 PRIMARY ENDPOINTS

7.4.1 Primary analysis of the primary endpoints

Primary analysis of the primary endpoints will be performed as defined in Sections 7.3.1 of the CTP.

The statistical model for the primary analysis defined in the CTP is an analysis of variance (ANOVA) model on the logarithmic scale including "treatment" as fixed effects and "subject" as random effect. Relative bioavailability of the study treatments will be estimated by the ratios of the geometric means of (T/R1) and (T/R2) of the primary endpoints.

Exclusion of PK parameters

The ADS ADPP contains column variables APEXC and APEXCO indicating inclusion/exclusion (APEXC) of a PK parameter and an analysis flag comment (APEXCO). All analyses based on the PKS are based on PK parameter values which are not flagged for exclusion, i.e. with APEXC equal to "Included".

Exclusion of plasma concentrations

The ADS ADPC (PK concentrations per time-point or per time-interval) contains column variables ACEXC or ACEXCO indicating inclusion/exclusion (ACEXC) of a concentration and an analysis flag comment (ACEXCO). Exclusion of a concentration depends on the analysis flag comment ACEXCO. For example, if ACEXCO is set to "ALL CALC", the value will be excluded for all types of analyses based on concentrations. If ACEXCO is set to "DESC STATS" the value will be excluded from descriptive evaluations per planned time

point/time interval. If ACEXCO contains the addition "TIME VIOLATION" or "TIME DEVIATION", the value can be used for further analyses based on actual times. If ACEXCO is set to "HALF LIFE", the value will be excluded from half-life calculation only; the value is included for all other analyses. Excluded concentration itself will be listed in the CTR associated with an appropriate flag.

Further details are given in "Noncompartmental Pharmacokinetic / Pharmacodynamic Analyses of Clinical Studies" (4) and "Description of Analytical Transfer Files and PK/PD Data Files" (5).

7.4.2 Sensitivity analysis, subgroup analysis, exploratory analysis of the primary endpoint

The same statistical model as used for the primary analysis (Sections 7.3.1 of the CTP) will be repeated for the primary endpoints but with all sources of variation ("subject", "treatment") considered as fixed effects.

Furthermore, primary PK endpoints will be assessed descriptively. The analysis of standard PK parameters is performed according to BI standards (4).

7.5 SECONDARY ENDPOINTS

7.5.1 Key secondary endpoints

This section is not applicable as no key secondary endpoint has been specified in the protocol.

7.5.2 Secondary endpoints

This section is not applicable as no secondary endpoint has been specified in the protocol.

7.6.2 Safety parameters

Safety endpoints and tolerability will be analysed as described in [Section 7.8](#) of this TSAP.

7.7 EXTENT OF EXPOSURE

Descriptive statistics are planned for this section of the report.

7.8 SAFETY ANALYSIS

All safety analyses will be performed on the TS.

7.8.1 Adverse Events

AEs will be coded with the most recent version of MedDRA.

The analyses of AEs will be descriptive in nature. All analyses of AEs will be based on the number of subjects with AEs and not on the number of AEs.

For analysis, multiple AE occurrence data on the eCRF will be collapsed into one event provided that all of the following applies:

- All AE attributes are identical (lower level term, intensity, action taken, therapy required, seriousness, reason for seriousness, relationship, outcome, AESI)
- The occurrences were time-overlapping or time-adjacent (time-adjacency of two occurrences is given if the second occurrence started at most 1 hour after the first occurrence ended)

For further details on summarization of AE data, please refer to "Analysis and Presentation of Adverse Event Data from Clinical Trials" ([7](#)) and "Handling of missing and incomplete AE dates" ([3](#)).

The analysis of AEs will be based on the concept of treatment emergent AEs. That means that all AEs will be assigned to screening, on-treatment or follow-up phases as defined in [Section 6.1](#). AEs will be analysed based on actual treatments, as defined in [Table 6.1: 2](#)

An overall summary of AEs will be presented. This overall summary will comprise summary statistics for the class of other significant AEs according to ICH E3 ([8](#)) and for the class of AESIs.

CTP: *The following are considered as AESIs:*

- *Hepatic injury*
A hepatic injury is defined by the following alterations of hepatic laboratory parameters:
 - *An elevation of AST (aspartate transaminase) and/or ALT (alanine transaminase) ≥ 3 -fold ULN combined with an elevation of total bilirubin ≥ 2 -fold ULN measured in the same blood sample, or*
 - *Aminotransferase (ALT, and/or AST) elevations ≥ 10 fold ULN*

The investigator had to classify on the eCRF whether an observed AE was an AESI or not.

According to ICH E3 ([8](#)) AEs classified as "other significant" need to be reported and will include those non-serious and non-significant AEs

- (i) which are marked haematological or other lab abnormalities, or
- (ii) which were reported with "action taken = discontinuation" or "action taken = reduced", or
- (iii) which lead to significant concomitant therapy as identified by the Clinical Monitor/Investigator at a Medical Quality Review Meeting.

The frequency of subjects with AEs will be summarised by treatment, primary SOC and preferred term. AEs which were considered by the investigator to be drug related will be summarised separately. Separate tables will also be provided for subjects with SAEs, subjects with AESIs and subjects with other significant AEs (according to ICH E3 ([8](#))). AEs will also be summarized by maximum intensity.

The SOCs and preferred terms within SOCs will be sorted by descending frequency over all treatment groups.

For disclosure of AE data on ClinicalTrials.gov, the frequency of subjects with non-serious AEs occurring with an incidence of greater than 5 % (in preferred terms) will be summarised by treatment, primary SOC and preferred term. The frequency of subjects with SAEs will also be summarised.

For disclosure of AE data in the EudraCT register, the frequency of AEs, the frequency of non-serious AEs with an incidence of greater than 5 % (in preferred terms) and the frequency of SAEs will be summarized.

For support of lay summaries, the frequency of subjects with drug-related SAEs will be summarized by treatment, primary SOC and preferred term.

7.8.2 **Laboratory data**

The analyses of laboratory data will be descriptive in nature and will be based on BI standards "Display and Analysis of Laboratory Data" ([9](#)).

Analyses will be based on normalised values, which means transforming to a standard unit and a standard reference range. The original values will be analysed if the transformation into standard unit is not possible for a parameter.

Descriptive statistics of laboratory values over time and for the difference from baseline (see [Section 6.7](#)) will be provided. Frequency tables of changes between baseline and last value on treatment with respect to the reference range will be presented.

Unscheduled measurements of laboratory data will be assumed to be repeat measurements of the most recent scheduled measurement (e.g. for follow-up or confirmation of a particular value). Therefore, unscheduled measurements will be assigned to the planned time point of the previous scheduled measurement. Descriptive statistics will be calculated by planned time point based on the worst value of the subject at that planned time point (or assigned to that planned time point).

Possibly clinically significant abnormal laboratory values are only those identified either in the Investigator's comments or at the RPM at the latest. It is the Investigator's responsibility to decide whether a lab value is clinically significant abnormal or not. Standard or project-specific rules for flagging clinically significant values in an automated manner will not be applied in this study.

Clinically relevant findings in laboratory data will be reported as baseline conditions (prior to first administration of study treatment) or as AEs (after first administration of study treatment) if judged clinically relevant by the investigator, and will be analyzed as such.

7.8.3 **Vital signs**

The analyses of vital signs (blood pressure and pulse rate) will be descriptive in nature. Descriptive statistics of vital signs over time and for the difference from baseline (see [Section 6.7](#)) will be provided.

Unscheduled measurements of vital signs will be assigned to planned time points in the same way as described above for laboratory data. However, for vital signs, descriptive statistics will

be calculated by planned time point based on the last value of the subject at that planned time point (or assigned to that planned time point).

Clinically relevant findings in vital signs data will be reported as baseline conditions (prior to first administration of study treatment) or as AEs (after first administration of study treatment) if judged clinically relevant by the investigator, and will be analyzed as such.

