### **1.2.2.2 Clinical experience in humans**

- In a clinical trial, potential drug-drug interactions were investigated between memantine and dextromethorphan in healthy male volunteers. The trial was conducted in an open-label, randomized, parallel-group design [[P13-15942](#)]. In one group (N=23), subjects were administered memantine in an up-titration scheme from 5 mg to 20 mg (10 mg bid) to steady state, similar to the dosing regimen in the planned trial 1346-0039. Therefore, the safety profile from this group is described in more detail: The adverse events observed after the up-titration phase under during memantine monotherapy (10 mg bid for 11 days) included headache, somnolence,

Proprietary confidential information © 2019 Boehringer Ingelheim International GmbH or one or more of its affiliated companies

decreased appetite, and dry mouth. All AEs were mild to moderate, no severe AEs, no deaths or serious adverse events were reported. Clinically significant increased ALT values ranged from 50 to 156 U/L.

One subject was withdrawn from the trial during the uptitration phase due to adverse events. The subject experienced nine central nervous system (CNS) and gastrointestinal AEs after 10 days of memantine monotherapy (i.e. 2 days after starting with 5 mg bid); These AEs included lightheadedness, dizziness, insomnia, constipation, abdominal pain, nausea, and loose stools, as well as emotional lability.

- A double-blind, fixed-dose study in 78 patients with moderate to severe AD assessed the safety and tolerability of a memantine 20 mg once-daily regimen compared with a 10 mg dose taken twice daily. Further, a 1-step once-daily dose titration schedule was compared with the standard 3-step up-titration schedule. Safety analysis suggest that once-daily dosing of memantine is as well tolerated as twice-daily dosing and that the standard 3-step up-titration schema may be better tolerated than a 1-step up-titration regimen. These results are in alignment with the current dosing recommendation provided by the SmPC [[R18-3740](#), [R18-3739](#)] and are reflected in the design of this trial.

According to the current summary of product characteristics (SmPC) [[R18-3740](#), [R18-3739](#)] common side effects of memantine are somnolence, dizziness, headache, balance disorders, dyspnea, constipation, hypertension, elevated liver function tests, and drug hypersensitivity.

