#### ***Safety measures:***

- A thorough screening examination will ensure that only suitable healthy subjects will enter the study, for example subjects with
  - with high liver enzymes or history of or current liver disease
  - GFR < 80 ml/min
  - medical conditions or nutrition habits that may cause urine alkalizationwill be excluded from study participation.
- Close monitoring of
  - Adverse events
  - Safety lab (special focus on hepatic parameters, eGFR)
  - ECG and Vital signs (focus on blood pressure)
  - C-SSRS
- Prohibition to use drugs that may cause urine alkalization ([Section 4.2.2](#))
- Drugs, medical conditions or nutrition habits that may cause urine alkalization are not allowed
- As memantine may impact the ability to operate vehicles and/or machines, subjects are not allowed to drive a vehicle or operate machines during Visit 3 and 4
- Close medical surveillance for at least 25 hours post-dose on the day of first administration of BI 425809 and memantine, respectively, and for up to 49 hours post-dose after combined administration of BI 425809 and memantine

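### The only categorical laboratory table uses the last on-treatment value, so a transient liver-test rise can miss both the shift table and the AE tables, and no stated table counts subjects by worst value

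*SAP*

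**What the plan says.** **Laboratory tables.** SAP 7.8.2 plans two kinds of summary. The first is continuous: "Descriptive statistics of laboratory values over time and for the difference from baseline". For these, unscheduled samples are assigned to the preceding scheduled time point, and "Descriptive statistics will be calculated by planned time point based on the worst value of the subject at that planned time point". SAP 7 fixes the statistics shown for continuous variables as N, mean, SD, minimum, median and maximum. The second is categorical: "Frequency tables of changes between baseline and last value on treatment with respect to the reference range will be presented". No worst-value shift table and no count by multiple of ULN is described.

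**Flagging and AESIs.** SAP 7.8.2 adds: "Standard or project-specific rules for flagging clinically significant values in an automated manner will not be applied in this study". Possibly clinically significant values are those the investigator comments on or that are identified by the report planning meeting. A laboratory finding becomes an AE only when the investigator considers it clinically relevant. Hepatic injury, the only AESI, is defined by fixed ULN multiples (Protocol 5.2.8.1.4, repeated in SAP 7.8.1), but for analysis "The investigator had to classify on the eCRF whether an observed AE was an AESI or not".

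**Why liver tests matter here.** The safety measures in Protocol 1.4 list "Safety lab (special focus on hepatic parameters, eGFR" among the items for close monitoring. Protocol 1.2.2.2 reports, from a group of healthy volunteers on a similar memantine up-titration: "Clinically significant increased ALT values ranged from 50 to 156 U/L".

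**The concern.** The protocol singles out hepatic parameters, yet the one table that classifies subjects as shifted or not keeps a single late value per subject and discards the rest. A rise that comes and goes is then counted as no shift. The AE tables are the other subject-level route, but they depend on the investigator's judgement of relevance and, for AESIs, on the investigator's classification. The SAP describes no programmed comparison with the measured values.

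At stake is the subject-level hepatic statement in the report: how many subjects had a raised liver test on BI 425809, on memantine and on the combination. The stated tables cannot answer that for rises that resolve.

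**Working it through.** **1. Samples that never reach the shift table.** Scheduled safety laboratory samples, read from the Flow Chart and its footnotes 10 and 14, by dosing period:

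| Period | Samples | Not used if last value is per period |
|---|---|---|
| BI 425809 alone | Days 2, 5, 9, 11 | 3 of 4 |
| Memantine alone | Days 7, 14, 21, 28, 35, and Visit 4 Day 1 (read as pre-dose) | 5 of 6 |
| Combination | Visit 4 Days 4 and 10 | 1 of 2 |

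The combination row is uncertain. The columns of the Visit 4 Day 11 discharge row cannot be aligned in the available text. If that row includes a laboratory sample, the figure is 2 of 3. The SAP also does not say whether the last value is taken per analysis phase or over the whole trial. If over the whole trial, 4 + 6 + 2 = 12 samples are drawn and 11 are unused. The counts are by dosing period. Table 6.1: 2 of the SAP assigns the first part of memantine dosing to the combined phase, so counts by analysis phase may differ.

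**2. Which rises are affected.** The documents give no ULN for ALT, so assume 35 to 50 U/L. The stopping criterion in Protocol 3.3.4.1 includes ALT or AST of at least 3 x ULN, which is 3 x 35 = 105 to 3 x 50 = 150 U/L. Affected rises lie between the ULN and that level. The cited range of 50 to 156 U/L corresponds to:
- lower end: 50/50 = 1.0 to 50/35 = 1.4 x ULN;
- upper end: 156/50 = 3.1 to 156/35 = 4.5 x ULN.

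Most of the cited range is therefore below the stopping level, and its top is above it.

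**3. Illustration (assumed data).** Sixteen subjects have ALT 25 U/L throughout. One rises to 100 U/L at a middle visit (100/50 = 2.0 to 100/35 = 2.9 x ULN) and is back at 25 at the last on-treatment sample.
- Last-value shift table: 0 of 16 to high.
- Worst-value shift table: 1 of 16.
- By-time-point table for that visit: mean (15 x 25 + 100)/16 = 29.7, median 25, maximum 100. With one value differing by d from n - 1 equal values, SD = d/√n = 75/4 = 18.75.

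With 156 U/L instead of 100, the shift results are the same (0 against 1 of 16). The visit statistics become mean 33.2, SD 131/4 = 32.75, median 25, maximum 156.

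**4. What the visit maximum cannot show.** Compare two cases, both normal at the last sample: (a) one subject at 100 U/L at two middle visits; (b) two different subjects at 100 U/L, one at each visit. Each visit has mean 29.7, SD 18.75 and maximum 100 in both cases, and the last-value shift table shows 0 of 16 in both. The number of affected subjects is 1 of 16 (6.25%) in (a) and 2 of 16 (12.5%) in (b). Only a worst-value or threshold count, or a reading of the listings, separates them.

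**The case against.** The strongest reply is that the plan already has several other routes by which a rise is seen.

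- **By-time-point statistics.** They use the subject's worst value at each time point, include unscheduled repeats, and print the maximum. This stands. A reader might infer that transient rises vanish from the safety tables or survive only in listings. The documents do not support that.
- **Listings.** Protocol 7.3.4 highlights every out-of-range value whatever the investigator's judgement, and SAP 7 lists all individual values. With 16 subjects these can be read by eye. This stands, but a listing is not a count by treatment.
- **Larger rises.** ALT or AST of at least 3 x ULN is a stopping criterion. AEs with discontinuation, and AEs that are marked laboratory abnormalities, go into the separate table of other significant AEs (SAP 7.8.1). This largely stands, so the gap concerns smaller rises.
- **AESI classification.** A reader might take 156 U/L as a case that the investigator's classification could hide. It is not one. On the assumed ULN it is below 10 x ULN, and without bilirubin of at least 2 x ULN in the same sample it is not an AESI at all.
- **Expected pattern.** A reader might also infer that a transient rise is what the documents predict. They report raised ALT on memantine but not its time course. A rise that persists to the last sample is caught by the planned table.
- **Sponsor standard.** SAP 7.8.2 cites a laboratory display standard that was not available and may specify further outputs. This limits the point to what the SAP itself states.

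None of these routes gives the number of subjects with a raised liver test at any time on each treatment.

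**Conclusion.** The point holds in a limited form. A liver-test rise that is below the stopping criterion, not judged clinically relevant, and normal by the last on-treatment sample is absent from the shift table and the AE tables. It is visible as a visit maximum and as a highlighted listing value. No stated table counts subjects by worst on-treatment value, and no stated step compares AESI classifications with the laboratory data.

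The size is 0 of 16 against 1 of 16 for each such subject. By dosing period, 3 of 4, 5 of 6 and about 1 of 2 scheduled samples are unused by the shift table, subject to the unclear Day 11 row and to a per-period reading. The ULN range and the ALT values in the illustration are assumptions; the 0 against 1 result needs only that the rise exceeds the ULN and resolves before the last sample.

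The change is worth making. Exclusion criterion 27 requires normal liver tests at screening, so a later high value is very likely new and a baseline-to-worst table is easy to interpret. The SAP already takes the worst value within a time point and gives no reason for taking the last value across time points. Consequences are confined to descriptive safety reporting.

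**What to change.** In SAP 7.8.2:

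1. Add a shift table from baseline to worst on-treatment value, by analysis phase and including unscheduled samples, for ALT, AST, total bilirubin and creatinine. Keep the last-value table as secondary.
2. State that on treatment is taken per analysis phase as defined in Table 6.1: 2.
3. Add programmed counts of subjects, by analysis phase, at the thresholds the protocol already contains: ALT or AST at least 3 x ULN and at least 10 x ULN, total bilirubin at least 2 x ULN, and ALT or AST at least 3 x ULN with bilirubin at least 2 x ULN in the same sample.
4. Reconcile those counts with the eCRF AESI classification before database lock.

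The shift table covers rises below the stopping level; the threshold counts check those at or above it. The cost is SAP wording and one or two extra tables from data already collected, with no new samples and no protocol amendment. The downside is that worst-value tables may look slightly less favourable. If the sponsor's display standard already produces these outputs, a sentence in the SAP saying so would be enough for items 1 and 3.
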